5.8 Intraocular Pressure

The N, mean, standard deviation, minima, median, and maxima for change in Intraocular Pressure (IOP) from Protocol TMI-09-01 baseline will be obtained by treatment group using the MEANS procedure and presented for each XT scheduled study visit, along with a 95% confidence interval on the mean change.

The number and proportion of subjects who are not using ocular hypotensive medication with $\geq 20\%$ reduction in IOP from baseline in the COMPASS Trial will be summarized by treatment group using the FREQ procedure and also presented at each XT study visit, along with 95% confidence intervals. In order to interpret changes to be reported in the previously described table, the number of ocular hypotensive medications used at Protocol TMI-09-01 screening, 12 month, and 24 month visits, and at each XT scheduled visit, as well as changes from each visit from screening will be summarized by treatment group. Finally, the number and proportion of subjects who are not using ocular hypotensive medication with IOP ≥ 6 mmHg and ≤ 18 mmHg will be presented at each study visit, along with an exact Clopper-Pearson 95% confidence interval from the FREQ procedure.

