4.2 Protocol Background and Rationale

Protocol TMI-09-01, also known as the COMPASS Trial, was a prospective, randomized, comparative multicenter study to assess the safety and effectiveness of the CyPass Micro-Stent in subjects with primary open angle glaucoma who were undergoing cataract surgery. In the study, a total of 505 subjects were randomized to one of two treatment groups, as follows: The CyPass group underwent cataract surgery and received the CyPass Micro-Stent, while the Control group underwent cataract surgery alone. All subjects randomized were followed for 2 years postoperatively.

The study was performed in 2 phases. During the initial phase, 75 subjects were randomized. After FDA review of 3 month or longer postoperative data on these subjects, approval was granted for enrollment and randomization of the remaining 430 subjects in the study expanded phase. Enrollment in the initial study phase began in September 2009 and ended in August 2010. Enrollment in the expanded phase of the study began in July 2011 and the last study subject was randomized in March 2013.

**CYPASS® MICRO-STENT
PROTOCOL TMI-09-01-E VERSION G**

Subjects enrolled in the COMPASS Trial were examined at 2 preoperative visits to confirm eligibility for study participation. The first visit (Screening Visit) involved a comprehensive ophthalmic examination. Subjects qualifying after completion of the Screening Visit were required to discontinue use of ocular hypotensive medication, or “washout”, for a pre-established period to remove the medication from their system. After washout, subjects returned for a Baseline Visit during which they were re-evaluated and additional baseline data was collected to confirm continued eligibility. Subjects who qualified after the Baseline Visit were scheduled for cataract surgery. After completion of uncomplicated cataract surgery, subjects were randomized intraoperatively to either the CyPass group or the Control group. Subjects were asked to return for examination at postoperative Day 1, Week 1, Month 1, Month 3, Month 6, Month 12, Month 18 and Month 24.

Study protocol TMI-09-01-E, the COMPASS Extension Trial, is designed to collect safety data beyond 24 months postoperatively for subjects who completed study protocol TMI-09-01. [REDACTED]
[REDACTED] Study enrollment was initiated April 2016.

**CYPASS® MICRO-STENT
PROTOCOL TMI-09-01-E VERSION G**

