5.1.3 Secondary Outcomes – Effectiveness

- Mean change in intraocular pressure (IOP)
- Proportion of subjects who are not using ocular hypotensive medication with $\geq 20\%$ reduction in IOP from baseline in the COMPASS Trial
- Proportion of subjects who are not using ocular hypotensive medication with IOP ≥ 6 mmHg and ≤ 18 mmHg

**CYPASS® MICRO-STENT
PROTOCOL TMI-09-01-E VERSION G**

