8.4 Subject Disposition

8.4.1 Discontinued Subjects

Subjects who exit the study prior to completion are considered to be “discontinued”. Subjects may be discontinued due to:

- Onset or progression of systemic disease that, in the opinion of the investigator, would put the subject’s health at risk or compromise the subject’s ability to return for necessary follow-up visits, or
- Administrative reasons (e.g., voluntary withdrawal or loss to follow-up)

The sponsor should be promptly notified of subject discontinuation and the relevant eCRF should be completed for this subject.

If a subject does not return for a scheduled study visit, the investigational site will make a minimum of 3 documented attempts via telephone, email, or regular mail to contact the subject. If the subject does not reply to any of these attempts, the site will send a letter to the subject using certified mail, with a request for notification of receipt. If a subject continues to be non-responsive to these follow-up attempts, the subject will be considered to be lost to follow-up.

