- CyPass device malposition or dislodgement, defined as CyPass positioning after deployment such that:
 - The device is not in the supraciliary space, or
 - There is a clinical sequela resulting from device position including, but not limited to:
 - Secondary surgical intervention to modify device position (e.g., repositioning, proximal end trimming or explantation)
 - Corneal endothelial touch by device
 - Corneal edema leading to loss of BCVA > 2 lines at the last postoperative visit in comparison with preoperative BCVA
 - Progressive ECL, defined as reduction in endothelial cell count of 30% or more relative to baseline ECD value
 - Erosion of device through sclera
 - Device obstruction requiring secondary surgical intervention.
- CyPass device exposure or extrusion
- Other events that necessitate unplanned intraocular surgical re-intervention (other than Nd:YAG capsulotomy), which includes, but is not limited to CyPass explantation, CyPass repositioning, CyPass trimming, planned CyPass lumen occlusion and treatment of elevated IOP that is not satisfactorily managed using ocular hypotensive medication
- Significant ptosis
- Atrophy/phthisis
- Wound dehiscence, which is defined as persistent aqueous leak or fistula formation
- Vitreous hemorrhage
- Chronic ocular pain, which is defined as continuous pain documented at 2 visits at least 30 days apart not associated with a pre-existing condition
- Significant foreign body sensation

**CYPASS® MICRO-STENT
PROTOCOL TMI-09-01-E VERSION G**

- Any 2-point worsening of an ocular symptom questionnaire report to “severe” or “very severe”, which is not associated with a pre-existing condition

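### The two medication-free IOP proportions count an eye as meeting the outcome even if a later IOP-lowering procedure brought it there; a supplementary table would show how much this matters

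*SAP*

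**What the plan says.** Protocol 5.1.3 defines one of the two outcomes as "Proportion of subjects who are not using ocular hypotensive medication with IOP ≥ 6 mmHg and ≤ 18 mmHg"; the other replaces the pressure range with a reduction of at least 20% from the COMPASS baseline. Protocol 3.4.3 and 9.8 and SAP 1 and 5.8 use the same two conditions. SAP 5.8 presents the range outcome as "subjects who are not using ocular hypotensive medication with IOP ≥ 6 mmHg and ≤ 18 mmHg will be presented at each study visit". For the other it says that the "reduction in IOP from baseline in the COMPASS Trial will be summarized by treatment group using the FREQ procedure". Grouping by treatment is not repeated for the range outcome, but it is the natural reading.

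Protocol 10.1 lists among the expected ocular adverse events "Other events that necessitate unplanned intraocular surgical re-intervention", and its examples are "CyPass explantation, CyPass repositioning, CyPass trimming, planned CyPass lumen occlusion and treatment of elevated IOP that is not satisfactorily managed using ocular hypotensive medication". Protocol 8.4.1 gives two grounds for discontinuation: systemic disease, and "Administrative reasons (e.g., voluntary withdrawal or loss to follow-up" being the examples of the second. A secondary procedure on the study eye is not among them.

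SAP 5.8 adds a summary of the number of hypotensive medications to help interpret the 20% table. SAP 5.2 tabulates and lists adverse events. SAP 6 says that only observed data are used, without imputation.

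**The concern.** There are two main ways for an eye to reach an acceptable pressure when the original treatment was not enough: resumed medication and a further procedure. The two proportions treat the first as not meeting the outcome and have no rule for the second. By the stated definition, an eye in which medication failed, which was then operated on and came off drops, counts as meeting the outcome.

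A rate shown by treatment group is easily read as the performance of the original treatment. On that reading, each eye controlled by a later procedure overstates its group's rate. The reader could not correct for this from the planned output. The adverse-event tables count re-interventions but do not show which of those eyes also met the IOP criterion at a given visit, and the medication table says nothing about procedures.

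**Working it through.** **Is there a rule anywhere?** Setting the places side by side:

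- Outcome definitions (Protocol 3.4.3, 5.1.3; SAP 1): medication use and IOP only.
- Analysis text (Protocol 9.8; SAP 5.8): the same.
- Missing data (SAP 6): covers absent values, not values measured after a procedure.
- Discontinuation (Protocol 8.4.1): does not remove these eyes.
- Protocol Appendix 2 is not visible in the text available, but both documents describe it as examination methodology.

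So the text contains no rule, and the eyes stay in the analysis as observed.

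**Is there a figure to reproduce?** No. The plan gives no expected proportion, procedure rate or powered sample size. SAP 4 states that no hypotheses are tested, and 480 is a ceiling (SAP 3).

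**Size in one group.** Let q be the share of a group's evaluable eyes with a later IOP-lowering procedure, and r the share of those that are off medication and meet the IOP criterion. The as-observed rate exceeds the rate with those eyes counted as not meeting the outcome by q × r. Both q and r are assumptions:

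- q = 0: 0 points, whatever r is.
- q = 2%, r = 25%: 0.02 × 0.25 = 0.5 points.
- q = 5%, r = 50%: 0.05 × 0.50 = 2.5 points.
- q = 10%, r = 50%: 0.10 × 0.50 = 5.0 points.
- q = 10%, r = 80%: 0.10 × 0.80 = 8.0 points.

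At an assumed 240 eyes per group (480/2; the protocol gives no allocation ratio), one eye is 100/240 = 0.42 points and the top of the range is 0.08 × 240 = 19.2 eyes.

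**Illustration.** Take an assumed observed rate of 144/240 = 60.0%, with exact Clopper-Pearson 95% CI 53.5-66.2%.

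| q | r | eyes moved | rate | 95% CI |
|---|---|---|---|---|
| 2% | 50% | 2 | 142/240 = 59.2% | 52.7-65.4% |
| 5% | 50% | 6 | 138/240 = 57.5% | 51.0-63.8% |
| 10% | 50% | 12 | 132/240 = 55.0% | 48.5-61.4% |
| 10% | 75% | 18 | 126/240 = 52.5% | 46.0-59.0% |

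**Between groups.** With the same r in both, the observed difference shifts by r × (q in one group − q in the other). This is 0 if q is equal, 0.50 × (0.05 − 0.02) = 1.5 points at 5% against 2%, and 0.75 × (0.10 − 0.02) = 6.0 points at 10% against 2%. The group with more procedures is the one flattered, and the documents do not say which that would be.

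**Denominator.** If the supplementary table kept only eyes with IOP and medication data at the visit, an eye already known to have had a procedure would drop out when its IOP was missing. Adding m such eyes gives (x − k)/(n + m), where x is the number meeting the outcome and k the number moved. With x = 144, k = 6, n = 240 and an assumed m = 2, this is 138/242 = 57.0% instead of 57.5%.

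**Can procedures be dated?** Protocol 4.2 puts the start of initial-phase enrolment in September 2009, the last randomisation in March 2013 and the start of extension enrolment in April 2016. That is 79 to 37 months after randomisation, or 55 to 13 months after month 24 (79 − 24 and 37 − 24). "During the initial phase, 75 subjects were randomized", and enrolment in that phase ended in August 2010. Sixty months later is August 2015, and the 90-day window then closes in November 2015, before the extension opened. Protocol 8.2.3 allows such data to be taken from charts, where available.

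**The case against.** The strongest reply is that this is a choice of target, not an error. The outcome is a status at a visit, both documents define it identically, and neither calls it control by the original treatment alone. The study is observational, its purpose is safety, and these outcomes are secondary and descriptive. All of that stands, and it is why the planned tables should stay. A reader might infer that the planned proportion is wrong or departs from the protocol; the documents do not support that.

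It is also fair that re-interventions are already disclosed. SAP 5.2 gives counts, percentages, intervals and listings, so a reader can roughly bound the reported intraocular part. The link to the IOP outcome by eye and visit is still missing.

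Mean IOP change has no procedure rule either. But that summary also takes medicated eyes as they are, so it treats both routes alike. The proportions exclude one route and admit the other.

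Finally, the size rests wholly on assumed values, and much of the range is modest beside the interval for a single group. That limits the importance of the point. It does not remove it, because the shift within a group goes one way only and a confidence interval does not cover it.

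**Conclusion.** The gap is real and minor. As written, both proportions count an eye controlled by a later procedure as meeting the outcome, so they can overstate control by the original treatment. The overstatement is 0 to about 8 points in a group, assuming that 0-10% of eyes had a procedure and 25-80% of those met the criterion. Zero belongs in the range because the documents do not show that any such eye exists.

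A reader might go further and infer that the comparison favours one group. The documents do not support this: they give no procedure rate for either group, and the SAP plans no between-group interval or test for these outcomes. The supported conclusion is that a supplementary table is a cheap, optional improvement.

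**What to change.** Keep the as-observed tables and add to SAP 5.8:

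> Both proportions will also be presented by treatment group with a study eye counted as not meeting the outcome at every visit after any secondary surgical or laser procedure to lower IOP on that eye, not counting the index surgery. The list of qualifying procedures will be fixed before analysis. The denominator is all study eyes with IOP and medication data at the visit, plus eyes still in follow-up with a prior qualifying procedure. The number of eyes with a qualifying procedure will be shown by treatment group and visit.

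The index surgery must be excluded explicitly. Protocol 4.2 says that after uncomplicated cataract surgery "subjects were randomized intraoperatively to either the CyPass group or the Control group", so a rule counting any procedure after randomisation would catch the CyPass implantation itself.

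The cost is a few extra tables, a procedure list agreed in advance and a check of procedure dates. The supplementary rates will be equal to or lower than the as-observed ones. Sources are the parent-trial data for procedures up to month 24, and in the extension the adverse-event forms, unscheduled-visit forms and medical history updates. They may be incomplete. The adverse-event entry concerns intraocular surgery and may not take in laser, the visible text does not show that the reason for a device procedure is recorded, and some data between month 24 and extension enrolment come only from charts, if available. A footnote should say so, because the supplementary rate may itself miss procedures.

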6. METHODS FOR HANDLING MISSING DATA

Since this is a safety observation study, no imputations of the data will be made. All tables and figures will be generated using observed data only.
